20.4.9 Handling of Missing Data

No missing data will be imputed in this study. All analyses will be performed using observed data.

21. Ethics and Protection of Human Subjects

21.1 Ethical Standard

As the Sponsor of this study, Biosense Webster has the overall responsibility for the conduct of the study, including assurance that the study meets the regulatory requirements of the Food and Drug Administration (FDA), applicable European medical device regulation and the local government. For study under MDR, MDR2017/745 will be applicable, amending Directive 2001/83/EC, Regulation (EC) No 178/2002 and Regulation (EC) No 1223/2009 and repealing Council Directives 90/385/EEC and 93/42/EEC.

The Sponsor will also maintain compliance with GCP (ICH E6 (R2), 9 November 2016), the European standard EN ISO 14155 (Clinical Investigation of Medical Devices for Human Subjects), the Declaration of Helsinki (Ethical Principles for Medical Research Involving Human Subjects, Fortaleza 2013), Sponsor general duties (21 CFR 812.40), selection of investigators (21 CFR 812.43), monitoring (21 CFR 812.46), supplemental applications (21 CFR 812.35 [a] and [b]), maintaining records (21 CFR 812.140 [b]), and submitting reports (21 CFR 812.150 [b]), and to local regulations where required.

- **General Duties**
Biosense Webster's general duties consist of submitting the clinical investigation application to appropriate regulatory agencies, assuring that sites have received EC approvals prior to shipping the devices, selecting investigators, ensuring proper clinical site monitoring and ensuring subject informed consent is obtained.
- **Data Quality and Reporting**
Biosense Webster is responsible for providing quality data that satisfy federal regulations and informing proper authorities of serious unanticipated AEs and deviations from the protocol.
- **Selection of Investigators**
All potential investigational sites will undergo an evaluation to ensure that the site has the appropriate facilities and personnel to conduct the study in compliance with the clinical investigational plan. Based on outcome of evaluation process, Biosense Webster will select qualified investigators, ship devices only to participating investigators, obtain a signed Investigator's Agreement and provide the investigators with the information necessary to conduct the study.
- **Supplemental Applications**
As appropriate, Biosense Webster will submit changes in the Clinical Investigational Plan to the investigators to obtain all applicable re-approvals.

- **Maintaining Records**
Biosense Webster will maintain copies of correspondence, data, adverse device effects and other records related to the study. Biosense Webster will maintain records related to the signed Investigator Agreements.
- **Submitting Reports**
Biosense Webster will submit any required regulatory reports identified in this section of the regulation. This may include UADEs, withdrawal of EC approval, current investigators list, annual progress reports, recall information, final reports and protocol deviations.

21.2 Informed Consent Process

21.2.1 Informed Consent Procedure and Documentation

Subjects informed consent must be obtained and documented according to the principles of informed consent in the latest version of the Declaration of Helsinki (Fortaleza, 2013), ISO 14155, and approved by the reviewing CA and EC.

Informed consent is mandatory and must be obtained from all subjects prior to their participation in the study.

Prior to screening or performing any study related procedures that are solely for the purpose of determining eligibility for this study, any potential benefits and risks of the study must be explained to the subject. Subjects will be informed about aspects of the study that are relevant to the subject's decision to participate. Subjects should be made aware that by signing the ICF, they are granting approval for study personnel to review their medical records and to collect/analyze personal medical information. Subjects should also be informed that study personnel will maintain confidentiality of the medical records at all times.

The ICF will be written in a native, non-technical, language that is understandable to the subject and is to be approved by the applicable EC prior to enrolling subjects. The subject or designee will be provided with ample time to read and understand the ICF and to consider participation in the study. Informed consent will be requested prior to enrollment and must be personally signed and dated by the subject, or subject's legal representative, prior to performance of any study related activity or procedure. If a subject is unable to read or write, informed consent shall be obtained through the aid of an independent witness who will be present throughout the process. The written ICF and any other information shall be read aloud and explained to the prospective subject and, whenever possible, subject shall sign and date the ICF. The witness must also sign and date the ICF attesting that the information was accurately explained, and that informed consent was freely given. The point of enrollment corresponds with the time that subjects signs the informed consent.

The investigator and/or designee must also clearly document the process of obtaining informed consent in the subject's source documents. The voluntary process of obtaining informed consent confirms the subject's willingness to participate in the study. It's the investigator's responsibility to ensure that the informed consent process is performed in accordance with ICH-GCP and, where applicable, local and federal regulations. Subjects should not be coerced, persuaded, or unduly influenced to participate or continue to participate in the trial. Subjects or his/her legal representative must be given ample time and opportunity to inquire about details of the trial and all questions about the trial should be answered to the

satisfaction of the patient or the representative. Failure to provide written informed consent renders the subject ineligible for the study. If new information becomes available that can significantly affect a subject's future health and/or medical care, this information shall be provided to the subject(s) affected in written form. If relevant, all affected subjects shall be asked to confirm their continuing informed consent in writing by dating and signing the amended ICF.

21.3 Participant and Data Confidentiality

During this clinical investigation, all representatives of the Sponsor will comply with all in-country privacy laws and regulations regarding contact with subjects, their medical record information, copying of information, and protection of the subject identities.

All information and data sent to Biosense Webster concerning subjects or their participation in this clinical investigation will be considered confidential. Only authorized Biosense Webster personnel or representatives (including contracted service providers, i.e. Core Lab, Clinical Research Associate, CRO, etc.), representatives of the FDA or CAs acting in their official capacities will have access to these confidential files upon request (including, but not limited to, laboratory test result reports, ECG reports, admissions/discharge summaries for hospital admission occurring during a patient's study participation and autopsy reports for deaths occurring during the clinical investigation). Some of the countries to which the study subjects and investigators personal data may be transferred may not offer as comprehensive a level of protection of personal data as within the European Union but Sponsor will take all reasonable steps to ensure a sufficient level of data protection. All data used in the analysis and reporting of this evaluation will exclude identifiable reference to the subject.

21.3.1 Research Use of Stored Data

- Intended Use: Data collected under this protocol may be used to study AF.
- Storage: Access to stored data will be limited. Data will be stored using codes assigned by the sponsor. Data will be kept in password-protected computers. Only investigators and the sponsor will have access to the data.

22. Source Documents and Access to Source Data/Documents

Data entered on to the eCRFs will be taken from source documentation, such as hospital procedure reports, admission and discharge summaries, other hospital or investigator office/clinic documents, and system data (CARTO, generator system). If unique study parameters are not documented on standard hospital or office reports, a worksheet may be developed to record this information. The worksheet shall be signed by the PI or authorized designee and will serve as source document and as basis for monitoring the eCRFs. Electronic subject records will be considered as source documents on the condition that the hospital's database is a validated system. If this is not the case, electronic records should be printed and added to the subject's paper file. A print-out of a completed eCRF cannot be used as source documentation.

Investigators should maintain information in the subject's medical records, which corroborate data collected on the eCRFs. In order to comply with these regulatory requirements, at minimum, the following is a list of information that should be maintained.

- Medical history/physical condition of the study subject before involvement in the study sufficient to verify protocol selection criteria (if not already present).

- Dated and signed notes from the day of entry into the study including the study Sponsor (Biosense Webster), protocol number, clinical site, subject number assigned and a statement that consent to participate in the study was obtained.
- Dated and signed notes from each study visit with reference to the eCRFs for further information, if appropriate (for specific results of procedures and exams).
- Reports on AEs and their resolution, including supporting documents such as discharge summaries, EP lab reports, ECGs, lab results.
- Notes regarding protocol-required medication and prescription medications taken during the study (including start and stop dates).
- Notes on subject's condition upon completion of or withdrawal from the study.

Only authorized Biosense Webster personnel or representatives, authorized site personnel, local government authorities, or the FDA, acting in their official capacities, will have access to these confidential files.

23. Quality Assurance and Quality Control

Quality Control (QC) procedures will be implemented beginning with the data entry system and ongoing QC checks will be run on the database. Any missing data or data anomalies will be communicated to the site(s) for clarification/resolution.

Following written SOPs, monitors will verify that the clinical trial is conducted and data are generated, documented, and reported in compliance with the protocol, GCP, and the applicable regulatory requirements. If noncompliance is identified, Sponsor is required by regulation to implement measures to secure compliance.

The investigational site will provide direct access to all trial related sites, source data/documents, and reports for the purpose of monitoring and auditing by the sponsor, and inspection by local and CAs.

24. Data Handling and Record Keeping

24.1 Data Collection and Management Responsibility

The Sponsor will be responsible for all data management activities. These activities include development of an EDC system and utilizing a validated EDC system into which all study data will be entered. The Sponsor will be responsible for reviewing all data to ensure the overall integrity of the database.

24.1.1 Data Collection

eCRFs will be used to collect all subject data during this clinical investigation. eCRFs have been developed to capture the information outlined in this clinical investigation Plan. Modification to the eCRF will only be made if deemed necessary by the sponsor. Data on these eCRFs will be monitored (source verified) and the monitor will ask the site representative to correct if necessary, to match the source documents. All changes made to the data will be tracked in the electronic audit trail. The investigator will be required to sign designated eCRFs as verification that they have been reviewed and the data entered are correct. Data from these eCRFs will be used to provide analysis of this clinical investigation.

24.1.2 Data Reporting

The investigator, or a designated individual, is responsible for ensuring that clinical investigation data are timely and properly recorded on each subject’s eCRF and related documents. The investigator, or a designated individual, is required to electronically sign the eCRF on the appropriate pages to verify that he/she has reviewed and attests to the correctness of the recorded data. Completed eCRF will be reviewed and monitored by the sponsor personnel, or an appropriately qualified and trained designee, throughout the clinical investigation. To this end, the Investigator and institution must permit inspection of the trial files and subject eCRFs by such representatives and/or responsible government agencies.

Investigators are required to prepare and submit accurate and timely reports on this study to the governing EC and Biosense Webster.

Table 9: Responsibilities for Preparing and Submitting Reports

Type of Report	Prepared by Investigator For	Time of Notification
Subject withdrawal	Biosense Webster	Should report within 5 working days
Withdrawal of EC approval	Biosense Webster	Should report within 5 working days
Final report	Biosense Webster, EC	Will prepare a final report for the clinical investigation as required per national regulations.
Informed consent not obtained from subject	Biosense Webster, EC	Should report within 5 working days

It is recommended that all eCRF data be entered by the designated site personnel as soon as possible. For AE reporting, refer to the Adverse Event Reporting Requirements and timelines noted within this clinical investigation protocol.

24.1.3 Data Verification and Review

Biosense Webster will track the amount of missing data and contact sites as appropriate to instruct them on steps to minimize missing data and remain compliant with protocol required assessments. Missing or unclear data will be queried as necessary throughout the trial. Biosense Webster will request further documentation such as physician and/or cardiac EP lab procedure notes when complications or device malfunctions/complaints are observed and reported. Biosense Webster will be responsible for auditing the database and confirming the overall integrity of the data.

24.1.4 Final Data Analysis

All exported datasets for analyses will undergo a final data review before final database lock. Once all critical data are monitored and locked, the final analyses of clinical investigation data will be performed.

24.2 Study Record Retention and Archiving

Records and reports for the study will remain on file at the site for a minimum of 5 years or per country specific record retention requirements following notification by the sponsor that all investigations have been terminated or completed. This documentation must be accessible upon request by the CAs, the sponsor, or a designee. The sponsor must approve archiving,

transfer, and destruction of the documentation, in writing, prior to the actual archiving, transfer, and destruction. The investigator must notify the sponsor, in writing, of transfer location, duration, and the procedure for accessing the study documentation.

If the investigator retires, relocates, or withdraws from assuming primary responsibility for keeping the study records, custody transfer per written notice must be submitted to the sponsor indicating the name and address of the person accepting primary responsibility. The EC must be notified in writing of the name and address of the new custodian. Record retention dates must be provided to all parties by the sponsor's corporation.

25. Study Suspension or Termination

This study may be temporarily suspended or prematurely terminated at the discretion of the Sponsor. The Sponsor may also terminate a site prior to study completion if the Sponsor believes the site is no longer capable of participating (e.g., cannot fulfill subject enrollment or protocol compliance goals, site suspension by EC). If the study is prematurely terminated or suspended, the PI will promptly inform the EC and will provide the reason(s) for the termination or suspension.

If suspension or premature termination occurs, the terminating party shall justify its decision in writing and promptly inform the other parties with whom they are in direct communication. The PI and sponsor shall keep each other informed of any communication received from either the EC or the CA.

If early termination of the study is required due to safety concerns, each site will undergo a monitoring visit to conclude any outstanding issues, collect all outstanding CRF information, verify device accountability, and discuss any other items relevant to the conclusion of the study. Any enrolled subjects will continue to be followed per the study protocol requirements.

If, for any reason, the sponsor suspends or prematurely terminates the study at an individual study site, the sponsor shall inform the responsible CA as appropriate and ensure that the EC is notified, either by the PI or by the sponsor. If the suspension or premature termination was in the interest of safety, the sponsor shall inform all other PIs.

Circumstances that may warrant termination or suspension include, but are not limited to:

- Determination of unexpected, significant, or unacceptable risk to participants
- Demonstration of efficacy that would warrant stopping
- Insufficient compliance to protocol requirements
- Data that are not sufficiently complete and/or evaluable
- Determination of futility

Study may resume once concerns about safety, protocol compliance, data quality is addressed and satisfy the sponsor, EC and regulatory agency.

26. Data and Publication Policy

Publications and/or presentation of clinical investigation results will be coordinated and governed between Biosense Webster, Inc., the clinical investigation author(s) and if applicable local law. Authorship will be determined prior to development of any manuscript. All information concerning the study, investigational medical device, sponsor operations, patent application, manufacturing processes, and basic scientific data supplied by the sponsor to the

investigator and not previously published, are considered confidential and remain the sole property of the sponsor.

27. Document Filing

A copy of all approved versions of the Investigation Protocol will be kept, by the site, in the Investigator Site File and in the Sponsor Trial Master File.

28. Scientific References

1. Bick, R.L. and E.P. Frenkel, *Clinical aspects of heparin-induced thrombocytopenia and thrombosis and other side effects of heparin therapy*. Clin Appl Thromb Hemost, 1999. **5 Suppl 1**: p. S7-15.
2. Cox, B., M.E. Durieux, and M.A.E. Marcus, *Toxicity of local anaesthetics*. Best Practice & Research Clinical Anaesthesiology, 2003. **17**(1): p. 111-136.
3. Gruchalla, R.S., *10. Drug allergy*. Journal of Allergy and Clinical Immunology, 2003. **111**(2): p. S548-S559.
4. Mertes, P.M. and M.C. Laxenaire, *Allergic reactions occurring during anaesthesia*. Eur J Anaesthesiol, 2002. **19**(4): p. 240-62.
5. Morcos, S.K., et al., *Prevention of generalized reactions to contrast media: a consensus report and guidelines*. Eur Radiol, 2001. **11**(9): p. 1720-8.

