18.3 Device Returns

All investigational devices (**used and unused**) will be returned to the Sponsor’s attention and per Sponsor’s Instructions. Device deficiencies should be properly documented on the eCRF. Any suspected malfunctioning device or device associated with an AE (device related AE) will undergo a thorough complaint analysis. All returned devices must be properly labeled with the study name, the subject identification number, date of issue, identified as a defective return, non-defective return, or AE (as applicable). All tracking information must be retained in the event the package has been lost and requires tracking. All investigational devices should be returned.

19. Clinical Monitoring

Clinical site monitoring is conducted to ensure that the rights and well-being of human subjects are protected, that the reported trial data are accurate, complete, and verifiable, and that the conduct of the trial is in compliance with the currently approved protocol/amendment(s), with GCP, and with applicable regulatory requirement(s). Each site will undergo periodic monitoring of the study, which involves a visit from a Sponsor representative, qualified to perform such visit. Monitoring visits may include, but are not limited to, the following:

- Protocol adherence
- Source documentation verification and accuracy of the eCRFs

- Verification that informed consent is being obtained for all subjects participating in the study in accordance with requirements described in the study protocol
- Verification of completeness of the site file
- Verification of accuracy of all study logs such as the Delegation of Responsibility Log, etc.
- Compliance with applicable regulations
- Identification and action to resolve any issues or problems with the study.

Data are to be submitted promptly via e-CRF after collection. Missing or unclear data will be corrected as necessary throughout the trial. Biosense Webster will request further documentation such as physician and/or cardiac EP lab procedure notes when complications or malfunctions are observed and reported.

Further details on clinical monitoring are provided in the study specific monitoring plan.

20. Statistical Methodology

The Sponsor will be responsible for the overall analysis of data from this protocol. This section represents the Statistical Analysis Plan for this protocol. All analyses and subsequent detail are described below.

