20.1 Levels of Significance

All data will be summarized by descriptive analyses. No formal statistical inference is planned. All confidence intervals will use the two-sided 95% confidence level unless otherwise stated.

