20.2 Sample Size Justification

A sample size of 30 subjects will allow characterization of the performance and safety of the OPTRELL™ catheter. Approximately 20 atrial and 10 ventricular procedures will be performed.

The sample size of 30 patients was selected based on previous experience with similar design in first in human assessments of multi-electrode mapping catheters. This study is meant to characterize the catheter's ability to perform safely in various types of arrhythmias. No clinical claims of effectiveness or patient outcomes will be made from this study.

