20.4.7 Analysis for Primary Endpoints

Primary Effectiveness Endpoint is defined as the completion of all pre-ablation mapping requirements and any clinically indicated mapping with the OPTRELL™ catheter without resort to non-study mapping catheter(s).

The primary effectiveness endpoint (success/failure) will be summarized using categorical summaries for the PP Analysis Set.

The number of subjects who started the pre-ablation mapping procedures with the OPTRELL™ catheter will be summarized overall, per chamber and by arrhythmia subgroup. The proportion of subjects who meet the requirements for success in the primary effectiveness endpoint will be summarized per chamber and overall.

A listing of the primary effectiveness endpoint will be provided.

Primary Safety Endpoint is defined as the incidence of serious adverse events related to the OPTRELL™ catheter within 7 days of index procedure. An SAE will be counted as related to the OPTRELL™ catheter if the relationship to a study catheter is anything other than 'Not Related'.

The number of subjects with SAEs related to the study catheter will be summarized in the Safety Analysis Set overall, by chamber and by each arrhythmia subgroup by Preferred Term and level of relationship. All tables will present summaries both by subject and by event.

If a subject has multiple occurrences of an event within a level of summarization, then for the by-subject summaries only a single occurrence will be counted at each level of summarization at the highest level of severity/relationship; for the by-event summary each event will be counted.

Device related SAEs will be defined and summarized similarly. All SAEs will be listed by System Organ Class and Preferred Term, severity, causality (defined as possible, probable or having a causal relationship to the device and/or procedure), anticipation and outcome.

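### Do the efficacy and futility stopping grounds in section 25 need a stopping rule in the descriptive analysis plan?

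*Combined protocol and SAP*

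**What the plan says.** Section 25 gives the stopping decision to the sponsor: "This study may be temporarily suspended or prematurely terminated at the discretion of the Sponsor". It then offers a list, expressly not exhaustive, of circumstances that may justify termination or suspension. Two of the five entries are "Demonstration of efficacy that would warrant stopping" and "Determination of futility". The other three concern risk to participants, protocol compliance and data quality. None of the five carries a threshold, a time point or a deciding body.

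Section 20 opens with "This section represents the Statistical Analysis Plan for this protocol. All analyses and subsequent detail are described below". Within it:

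- Section 20.1: "No formal statistical inference is planned. All confidence intervals will use the two-sided 95% confidence level unless otherwise stated".
- Section 20.2 sets 30 subjects by precedent, about 20 atrial and 10 ventricular, and adds "No clinical claims of effectiveness or patient outcomes will be made from this study".
- Section 20.4.7: "The primary effectiveness endpoint (success/failure) will be summarized using categorical summaries for the PP Analysis Set". Section 20.4.1 defines such summaries as count and percent.

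On timing, section 24.1.4 says "Once all critical data are monitored and locked, the final analyses of clinical investigation data will be performed". The only review of data during enrolment is the review of aggregate safety data in section 15.5.

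**The concern.** Read literally, section 25 allows a stop because efficacy has been shown or has become unattainable, while section 20 supplies nothing by which either could be judged. There is no performance goal, look, boundary or interval tied to the primary effectiveness endpoint.

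The study is open-label and single-arm, and each subject's mapping success or failure is known when the procedure ends. The sponsor also runs the analysis. A stop on either ground would therefore be decided on accumulating results, and the reported proportion would depend on when the study stopped. An early stop would also shorten the safety record of a first-in-human study and could leave the planned atrial and ventricular numbers unfilled. Finally, stopping for efficacy seems to sit badly with the undertaking to make no effectiveness claims.

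**Working it through.** **1. No figure in the plan to reproduce.** The 30 subjects rest on previous experience. There is no alpha, power, target rate or precision, so there is no operating characteristic that an unplanned stop could spoil. With no test, there is no type I error to inflate.

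**2. Size of the effect under assumed rules.** The documents give no rule, so both rules below are assumptions. Let p be the true success rate.

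*Efficacy rule: stop if the first 10 procedures all succeed, otherwise continue to 30.* On stopping, the report is 100%. Had the study continued, the expected report would be (10 + 20p)/30. The bias in the mean is therefore p^10 × (20/30) × (1 − p).

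| p | Reports 100% under the rule, p^10 | Reports 100% with fixed 30, p^30 | Bias in the mean |
|---|---|---|---|
| 0.80 | 10.7% | 0.1% | +1.4 points |
| 0.90 | 34.9% | 4.2% | +2.3 points |
| 0.95 | 59.9% | 21.5% | +2.0 points |

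With the look at 15 and p = 0.90: 0.9^15 = 20.6%, and the bias is 0.206 × (15/30) × 0.10 = +1.0 point.

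*Futility rule: stop if 7 or fewer of the first 10 succeed.* At p = 0.80 the study stops 32.2% of the time and the mean report is 76.8% (−3.2 points). At p = 0.90 it stops 7.0% of the time and the mean is 89.0% (−1.0 point).

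*Both rules at 10.* Section 25 names both grounds together. The two rules fire on disjoint outcomes, so the biases add: +2.3 − 1.0 = +1.3 points at 90%, and +1.4 − 3.2 = −1.8 points at 80%.

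*Yardstick.* The exact two-sided 95% interval for 27/30 is 73.5% to 97.9%, or 24.4 points wide.

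**3. Would deleting the two entries remove the risk?** No. The discretion at the head of section 25 would remain, and the list says that it is not complete. The sponsor could stop on the same data on the same day, with the same effect on the reported proportion.

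**4. Is an early-stopped study reportable as the plan stands?** Largely yes:

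- Section 20.3 defines the Safety set by catheter insertion, and the PP set by eligibility and the start of mapping. Neither depends on reaching 30.
- Section 20.4.3 tabulates subjects screened, enrolled, in each set, completed and discontinued.
- Section 20.4.1 puts a count beside each percent, so 10/10 cannot pass for 30/30.
- Section 20.4.9 uses observed data only.
- Section 20.2 states the planned number, and section 25 requires written justification from the party that terminates.

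Only an explicit sentence setting planned against achieved numbers is absent. An analyst would supply it without instruction.

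**5. Is there a contradiction with section 20.2?** Not strictly. That section rules out clinical claims; a decision to stop enrolling is not a claim. Section 25 also does not tie efficacy or futility to the primary effectiveness endpoint, and futility could be operational. Its sentence on resuming the study mentions only safety, compliance and data quality, which suggests a generic list.

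**The case for a change.** The strongest case for acting is that permission is itself the problem: two outcome-based grounds are named in advance with no criterion, and the written justification comes only at the time of the stop. The descriptive proportion is the study's main effectiveness output. Although the bias in its mean is small, the chance of a perfect headline result rises markedly under the assumed efficacy rule (34.9% against 4.2% at a true 90%). An early stop would also weaken the safety picture: with no related SAEs, the exact two-sided 95% upper limit, 1 − 0.025^(1/n), is 30.8% at n = 10 against 11.6% at n = 30. Removing two entries costs almost nothing.

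The textual mismatch stands, and so does the arithmetic. What does not stand is the inference that an edit would protect the result. The exposure comes from the sponsor's general discretion, which deletion leaves untouched. The alternative, a stated criterion with looks, would bring decision-making on effectiveness into a study designed only to characterise performance. The perfect-score comparison sets 10/10 against 30/30, and the required count would show the reader which was obtained.

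The 95% level in section 20.1, which is attached to no endpoint, is a separate matter. It is a default for any interval that is reported, and whether the primary proportions should carry one does not turn on section 25.

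**Conclusion.** No change is needed. The efficacy and futility entries are loose wording, probably generic, in a permissive list. They are not a stopping rule, and no planned analysis relies on them. Removing them would be harmless tidying that alters no result and no one's authority to stop.

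Under the assumed rules with both grounds applied at 10 procedures, the mean reported success rate moves by +1.3 points at a true 90% and −1.8 points at a true 80%, small against an interval about 24 points wide at 27/30. These figures illustrate scale only, since the documents state no rule. The conclusion rests on the study remaining descriptive, with counts shown beside percentages and disposition reported as section 20.4.3 requires. If the sponsor did intend to stop on effectiveness results, or to draw a formal conclusion from the proportion, a criterion would be needed. Nothing in section 20 suggests either.
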